6.0 DATA AND SPECIMEN SUBMISSION

6.1 Data Collection and Submission

Data collection for this study will be done exclusively through the Medidata Rave clinical data management system. Access to the trial in Rave is granted through the iMedidata application to all persons with the appropriate roles assigned in Regulatory Support System (RSS). To access Rave via iMedidata, the site user must have an active CTEP-IAM account (check at [REDACTED] and the appropriate Rave role (Rave CRA, Read-Only, Site Investigator) on either the LPO or participating organization roster at the enrolling site.

Upon initial site registration approval for the study in RSS, all persons with Rave roles assigned on the appropriate roster will be sent a study invitation e-mail from iMedidata. To accept the invitation, site users must log into the Select Login [REDACTED] using their CTEP-IAM user name and password, and click on the “accept” link in the upper right-corner of the iMedidata page. Please note, site users will not be able to access the study in Rave until all required Medidata and study specific trainings are completed. Trainings will be in the form of electronic learnings (eLearnings), and can be accessed by clicking on the link in the upper right pane of the iMedidata screen.

Users who have not previously activated their iMedidata/Rave account at the time of initial site registration approval for the study in RSS will also receive a separate invitation from iMedidata to activate their account. Account activation instructions are located on the CTSU website, Rave tab under the Rave resource materials (Medidata Account Activation and Study Invitation Acceptance). Additional information on iMedidata/Rave is available on the CTSU members’ website under the Rave tab at [REDACTED] or by contacting the CTSU Help Desk at [REDACTED] or by e-mail at [REDACTED]

A Schedule of Forms is available on the Alliance study webpage, within the Case Report Forms section.

Patient-completed questionnaire booklets for this study are to be ordered prior to the registration of any patients (see Section 4.4). Samples of questionnaire booklets are available in Appendices I and II for reference and IRB submission only. They are not to be used for patient completion. Booklets must be given to patients to complete and patients should be instructed to return the booklets to site staff either in person or by mail and site staff will enter patient and caregiver responses into Rave.

7.0 STUDY IMPLEMENTATION

7.1 Identification of participating institutions

It is expected that a majority of participating institutions will be identified prior to the activation of this study. However, recruitment of additional institutions will continue following activation of the study. Interested sites should contact the study chair, [name] to discuss the criteria listed in Section 13.1.

7.2 Site training

Before enrolling patients, each site randomized to one of three intervention arms must determine their desired mode of delivery for the decision aids (either by desktop computer or tablet). Sites that opt for tablet delivery of the decision aid will receive a tablet from the investigative team: Either by shipment or by hand delivery, depending on whether or not a member of the study team travels to the participating institution to provide personnel training.

Site personnel will be trained on the process of data collection and delivery of the intervention prior to the enrollment of any patients. This training will be provided either by video/telephone conferencing or by on-site training. consist of either video training and telephone conferencing or on-site training. The content of the training will consist of co-developing or adapting site-specific standard operating procedures (SOPs) that accommodate local site environments while maintaining fidelity to the particular study arm to which sites have been randomized. Training will be provided by a member of the study team from Mayo Clinic.

7.3 Site scheduling and clinic space requirements

Scheduling: Sites will need to determine the time needed to complete registration, pre-consultation decision aid interaction (for applicable study arms), and post-consultation questionnaire completion. Study coordinators will need to schedule patients to be present at the study site for sufficient time to complete pre- and post-consultation study items. Alternatively, sites must identify processes for pre- and post-consultation study requirements to be completed in very close proximity (1 business or less) to the visit.

Space requirements: Sites will need to identify and reserve an adequately private area near or adjacent to the patient waiting area. This space will be used to obtain patient consent for participation, obtain HIPAA authorization, and interact with the pre-consultation decision aid (for applicable study arms), and completion of the post-visit questionnaire.

Pre-consultation decision aid requirements: For study arms with the pre-consultation decision aid, this adjacent space must contain a computer terminal with internet access, or have wireless access provided to the room so that a tablet may be used.

During-consultation decision aid requirements: For study arms that will use the during-consultation decision aid, sites will need to ensure that exam rooms are provisioned with wireless internet access or contain a computer terminal with internet access. Either of these is needed in order for the physician to deliver the during-consultation decision aid.

Physician notification process: Sites should establish a local process for informing the participant's physician that the participant has completed pre-requisite study registration and intervention (where applicable). The physician will then be alerted to follow the during-consultation study procedures specific to his/her study site.

8.0**INTERVENTION**

While it is expected that registration will occur on the same day as the initial surgical consultation, the intervention (surgical consult visit) must occur within 14 days following registration. Registration may occur after the surgical consult visit and patient completion of the Baseline Questionnaire, but must be completed no later than the same day as the consultation.

Participating sites will be randomized to Pre- plus During-Consultation decision aids, Pre-consultation decision aid only, during-consultation only decision aid, or usual care arms.

Arm A	Pre- and During Consultation Decision Aids ^{1, 2}
Arm B	Pre-Consultation ² Decision Aid Only
Arm C	During Consultation ¹ Decision Aid Only
Arm D	Usual Care

1 “Prostate Choice”

2 “Knowing Your Options”

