4.4 Patient Registration/Randomization Procedures

Patient enrollment will be facilitated using the Oncology Patient Enrollment Network (OPEN). OPEN is a web-based registration system available on a 24/7 basis. To access OPEN, the site user must have an active CTEP-IAM account (check at [REDACTED]) and a 'Registrar' role on either the LPO or participating organization roster. Registrars must hold a minimum of an AP registration type.

All site staff will use OPEN to enroll patients to this study. It is integrated with the CTSU Enterprise System for regulatory and roster data and, upon enrollment, initializes the patient in the Rave database. OPEN can be accessed at [REDACTED] or from the OPEN tab on the CTSU members' side of the website at [REDACTED]. To assign an IVR or NPIVR as the treating, crediting, consenting, drug shipment (IVR only), or investigator receiving a transfer in OPEN, the IVR or NPIVR must list on their Form FDA 1572 in RCR the IRB number used on the site's IRB approval.

Prior to accessing OPEN, site staff should verify the following:

[figure not shown]
- All eligibility criteria have been met within the protocol stated timeframes.
- All patients have signed an appropriate consent form and HIPAA authorization form (if applicable).

Note: The OPEN system will provide the site with a printable confirmation of registration and treatment information. Please print this confirmation for your records.

Further instructional information is provided on the OPEN tab of the CTSU members' side of the CTSU website at [REDACTED]. For any additional questions contact the CTSU Help Desk at [REDACTED]

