8.1 Patient identification, scheduling, and consent

Sites should implement standard procedures for identifying eligible patients for this study. Patient eligibility will be determined locally by a combination of chart review and patient self-report. Clinical variables about the patients care germane to eligibility will be ascertained by site staff. Site staff must confirm with the patient that this is not a second opinion, and that this is the first face-to-face visit with the doctor to discuss treatment options. It is not required that patients know their diagnosis before the study is introduced to them.

Prospective patients who are informed about a new diagnosis of prostate cancer will be scheduled to receive a follow-up consultation with a physician to discuss treatment options. The scheduled prostate cancer consultation must be the first consultation after diagnosis (i.e. not a second-opinion or a consultation following previous discussions of treatment options). Physicians may consider referring patients to the study team for recruitment upon receipt of positive PCa biopsy results from the lab if the cancer diagnosis has already been disclosed by telephone or email.

It is critical that the site coordinator identify when this visit is scheduled, and plan to make contact (or arrange for the patient’s physician to make contact) with the prospective participant before their scheduled consultation and inform them about the study. Participating institutions should implement a procedure for alerting the study coordinator when an eligible patient has been scheduled for the initial consultation. Institutional study coordinators will document all contact with all potentially eligible participants and indicate interest/non interest or “not approached.”

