If the prospective participant expresses interest in the study, the study coordinator should instruct the patient to arrive at their consultation appointment early enough (as determined by site-specific standard operating procedures) to complete all study-related activities. Patient consent may be obtained at any time up to and including the day of the consultation, but must be completed prior to any study-related activities. In addition, for sites randomized to the pre-consultation decision aid, time should be allowed for sufficient and unhurried patient interaction with the pre-consultation decision aid. All participants should also be informed that they will need to remain after the appointment to complete a short questionnaire (Baseline Questionnaire, see Appendix I).

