8.2 Procedures for intervention on the day of the prostate cancer consult

8.2.1 Patient arrival

Following the completion of the consent and registration procedures, the study coordinator will greet and engage participant and escort them to a private area preferably near the waiting area.

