11.0 END OF INTERVENTION

11.1 Duration of Treatment

The study intervention will take place in one day and follow-up assessments will occur at 12 months following the intervention.

11.2 Managing ineligible patients and registered patients who never receive protocol intervention

Definition of ineligible patients

A study participant who is registered to the trial but does not meet all of the eligibility criteria is deemed to be ineligible.

Follow-up for ineligible patients who continue with protocol intervention

Patients who are deemed ineligible after registering may continue the protocol intervention, provided the treating physician, study chair, and executive officer agree there are no safety concerns if the patient continues protocol intervention. All tests and data submission are to continue as if the patient were eligible. Notification of the local IRB may be necessary per local IRB policies.

Follow-up for ineligible patients who discontinue protocol intervention

For patients who are deemed ineligible after registering to the trial, who start the study intervention, but then discontinue the intervention, the same data submission requirements are to be followed as for those patients who are eligible and who discontinue study participation.

Follow-up for patients who are registered, but who never start study intervention

For all study participants who are registered to the trial but who never receive study intervention (regardless of eligibility), baseline and off-treatment notice data submission required. See the Data Submission Schedule accompanying the All Forms Packet.

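### Section 8.0 lets sites register a man after the primary-outcome questionnaire, Sections 7.3 and 8.2.1 put registration first, and no visible text accounts for men consented but never registered

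*Combined protocol and SAP*

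**What the plan says.** Four parts of the protocol bear on when a man enters the trial.

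- **Section 8.0.** Registration is expected on the day of the consultation, and "the intervention (surgical consult visit) must occur within 14 days following registration". The next sentence adds that "Registration may occur after the surgical consult visit and patient completion of the Baseline Questionnaire", with the end of that day as the limit.
- **Section 7.3 (physician notification).** The physician is to be told that "the participant has completed pre-requisite study registration and intervention (where applicable"), and this alert starts the during-consultation procedures.
- **Section 8.2.1.** The day's procedures begin with registration already done: "Following the completion of the consent and registration procedures, the study coordinator will greet and engage participant".
- **Section 8.1.** Consent "must be completed prior to any study-related activities".

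According to the Study Calendar (Section 5.0) and Appendix I, the Baseline Questionnaire holds the Prostate Cancer Treatment Questionnaire. Section 12.2 makes that 12-item score the primary endpoint, measured once, straight after the consultation.

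Three passages bear on who is counted.

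- **Section 8.1** sets up a local log: "Institutional study coordinators will document all contact with all potentially eligible participants". It records contact and interest.
- **Section 4.4** says that OPEN, "upon enrollment, initializes the patient in the Rave database", so the central record begins at registration.
- **Section 11.2** covers men "registered to the trial but who never receive study intervention (regardless of eligibility), baseline and off-treatment notice data submission required".

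**The concern.** Under Section 4.3 every man at a site gets the site's arm, and under Section 7.2 staff are trained for that arm. If registration may follow the booklet, staff who know the arm can settle whether a man enters the trial after his primary outcome is on paper.

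This need not involve misconduct. Where registration comes first, a man who leaves before finishing the booklet is a registered participant with a missing primary outcome, and a man found ineligible at the visit falls under Section 11.2. Where registration comes last, either man may never appear in the central database. The visible text has a rule for men registered but never exposed. It has none for men exposed but never registered.

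If such losses were related to knowledge and differed between arms, the main-effect comparisons would be biased. Without counts of consented and registered men, a reader could not tell whether that had happened.

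**Working it through.** **Step 1: the passages side by side.**

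| Question | Section 8.0 | Sections 7.3 and 8.2.1 |
|---|---|---|
| Usual order | Same day, or up to 14 days before the visit | Registration before the visit |
| After visit and booklet? | Allowed, same day | Not mentioned |

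| Check | Direction | Covers consented but unregistered men? |
|---|---|---|
| Section 4.4, before OPEN | Registered men must have consented | No |
| Section 8.1 log | Contact and interest | Not by consent or registration status |
| Section 11.2 | Registered, never exposed | No |

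**Step 2: the plan's own figure.** Section 12.2.2 states about 85% power with 50 against 50 men, a difference of 8, SD 12 and two-sided alpha 0.025. The noncentral t with 98 df gives 85.3% and the normal approximation 86.3%, so the figure reproduces. It sets the scale below; the point does not depend on it.

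**Step 3: standard error at full enrollment.** Section 12.2.2 gives 172 men, 20 sites (172/20 = 8.6 men per site), an intra-site correlation of 0.1 and SD 12:

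SE = sqrt[(4 × 12² / 172) × (1 + 7.6 × 0.1)] = sqrt(3.349 × 1.76) = 2.43 points. The critical value is z = 2.2414.

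**Step 4: an illustration.** The loss rate p and the correlation r between score and being left unregistered are assumptions; the documents give neither. If the men lost are the lowest fraction p on a cue correlated r with score, the mean of an affected arm shifts by

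d = r × 12 × φ(z_p) / (1 − p).

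With r = 0.3:

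- p = 0.05: d = 0.3 × 12 × 0.1031 / 0.95 = 0.391
- p = 0.10: d = 0.3 × 12 × 0.1755 / 0.90 = 0.702

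If all three aid arms are affected, a main effect is biased by d − d/2 = d/2. If only the two arms sharing one aid are affected, that aid's main effect is biased by d. Type I error is 1 − Φ(2.2414 − bias/SE) + Φ(−2.2414 − bias/SE).

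| Loss pattern | p | Bias (points) | Share of 8 | Type I error |
|---|---|---|---|---|
| Three aid arms | 5% | 0.195 | 2% | 0.0255 |
| Three aid arms | 10% | 0.351 | 4% | 0.0265 |
| Two arms sharing one aid | 5% | 0.391 | 5% | 0.0269 |
| Two arms sharing one aid | 10% | 0.702 | 9% | 0.0311 |
| All four arms equally | either | 0 | 0% | 0.0250 |

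Loss unrelated to score (r = 0) gives no bias.

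**Step 5: check with clustering.** A simulation of 40,000 trials used 20 sites of 8 or 9 registered men, intra-site correlation 0.1, and site means tested by t on 17 df. In the order of the first four rows above, it gave biases of 0.18, 0.30, 0.37 and 0.65, with type I errors of 0.025, 0.026, 0.026 and 0.030. Monte Carlo error is about 2.43/sqrt(40,000) = 0.012 points for the bias and sqrt(0.025 × 0.975/40,000) = 0.0008 for the error rate. Equal loss in all four arms gave a bias of at most 0.017 and error rates of 0.024 to 0.027.

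**Step 6: number of men.** To register 43 men in an arm, a 5% loss means 43/0.95 − 43 = 2.3 men and a 10% loss 43/0.90 − 43 = 4.8 men. With five sites per arm that is about 0.5 or 1.0 man per site over the whole trial.

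**The case against.** A reader might infer that Section 8.0 contradicts itself. It reads more naturally as one window with a permitted exception: up to 14 days before, expected on the day, and never later than that day. What stands is that Sections 7.3 and 8.2.1 describe only the usual order and leave the exception out.

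A reader might also infer that sites can drop men with poor scores. The documents do not support that. No step in which site staff score the booklet is described, registration closes the same day, and consent forms, booklets and the contact log would leave a local trace. Section 13.1 asks each site for 8 to 10 men with minority minimums, so the incentive is to register everyone who consents.

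The numbers also favor the plan. The documents give no reason why loss would strike both arms sharing one aid but not the third aid arm. With all three aid arms affected, the simulated type I error of 0.025 to 0.026 cannot be told apart from the no-bias case.

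Finally, the finding that nothing covers these men rests on the text available. The Schedule of Forms (Section 6.1), the site operating procedures (Section 7.2) and the consent pages are not visible, and any of them could call for such a match. Sections 12.5.2 and 12.5.3 provide for recruitment meetings and calls on accrual and data completeness, but these do not require one.

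These objections limit the size of the point. They do not remove the permission in 8.0, the mismatch with 7.3 and 8.2.1, or the absence of a count in the visible protocol.

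**Conclusion.** The point holds as a minor one. Entry to the trial can be settled after the once-only primary outcome is recorded, at sites that know their arm. Two other sections describe a different order, and the visible text does not account for men who consented and were exposed but not registered.

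It does not follow that the primary result is compromised, or that consent may come late. The documents show no such loss and require consent first. With an assumed correlation of 0.3 and 5% to 10% loss in aid arms, the bias is about 0.2 to 0.7 points against a target of 8, and type I error rises from 2.5% to at most 3.11%. Equal loss in all arms, or loss unrelated to score, gives no bias. The reason to act is that the order is easily put right and the counts would let readers see that nothing was lost.

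**What to change.** In Section 8.0, delete the permission to register after the Baseline Questionnaire. Require OPEN registration before the pre-consultation aid or, in arms without it, before the consultation. Sections 7.3 and 8.2.1 then agree without further change.

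If same-day flexibility has to be kept for accrual, require that every man who signs consent is registered that day, whatever happens at the visit or with the booklet, and state the exception in 7.3 and 8.2.1. A man whom the Section 4.4 eligibility check prevents from being registered would appear in the count with that reason.

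In either case, report the numbers consented and registered by arm, with reasons for non-registration. The consent records and the Section 8.1 log can supply them.

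The cost is a short amendment and one table. A few men identified late on the day may be missed. The documents give no number for them, and the loss would matter most for American Indian/Alaska Native men, whose identification Section 1.5 names as the main limit on accrual. The loss is contained because OPEN is available around the clock, registration may precede the visit by up to 14 days, and consent already has to come first. Selection at approach and consent by staff who know the arm would remain; this change does not address it.

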8.1 Patient identification, scheduling, and consent

Sites should implement standard procedures for identifying eligible patients for this study. Patient eligibility will be determined locally by a combination of chart review and patient self-report. Clinical variables about the patients care germane to eligibility will be ascertained by site staff. Site staff must confirm with the patient that this is not a second opinion, and that this is the first face-to-face visit with the doctor to discuss treatment options. It is not required that patients know their diagnosis before the study is introduced to them.

Prospective patients who are informed about a new diagnosis of prostate cancer will be scheduled to receive a follow-up consultation with a physician to discuss treatment options. The scheduled prostate cancer consultation must be the first consultation after diagnosis (i.e. not a second-opinion or a consultation following previous discussions of treatment options). Physicians may consider referring patients to the study team for recruitment upon receipt of positive PCa biopsy results from the lab if the cancer diagnosis has already been disclosed by telephone or email.

It is critical that the site coordinator identify when this visit is scheduled, and plan to make contact (or arrange for the patient’s physician to make contact) with the prospective participant before their scheduled consultation and inform them about the study. Participating institutions should implement a procedure for alerting the study coordinator when an eligible patient has been scheduled for the initial consultation. Institutional study coordinators will document all contact with all potentially eligible participants and indicate interest/non interest or “not approached.”

If the prospective participant expresses interest in the study, the study coordinator should instruct the patient to arrive at their consultation appointment early enough (as determined by site-specific standard operating procedures) to complete all study-related activities. Patient consent may be obtained at any time up to and including the day of the consultation, but must be completed prior to any study-related activities. In addition, for sites randomized to the pre-consultation decision aid, time should be allowed for sufficient and unhurried patient interaction with the pre-consultation decision aid. All participants should also be informed that they will need to remain after the appointment to complete a short questionnaire (Baseline Questionnaire, see Appendix I).

